2. OBJECTIVES AND ENDPOINTS

This study will evaluate the safety, tolerability, PK, PD, and preliminary clinical activity of a single intravenous (IV) infusion of SBT777101 in adult subjects with RA that have failed two or more prior b/tsDMARDs. Specific objectives and corresponding endpoints of this study are described below.

Objectives	Endpoints
Primary	
To evaluate and characterize the safety and tolerability of SBT777101	 Incidence, nature, and severity of adverse events Incidence and nature of dose-limiting toxicities (DLTs) Change from baseline in targeted vital signs, clinical laboratory tests and ECG parameters
Exploratory	
To assess and characterize SBT777101 pharmacokinetic profile in peripheral blood and synovium	Peripheral blood CAR transgene PK parameters including, but not limited to, T _{max} , C _{max} , AUC ₀₋₂₈ , and C _{last}

	Presence of SBT777101 in synovial tissue and/or fluid
To assess and characterize SBT777101 mechanism of action and pharmacodynamic parameters in peripheral blood and synovium	 Levels of inflammatory cells and biomarkers in synovial tissue and/or fluid pre-dose and following SBT777101 administration Levels of systemic markers of inflammation in peripheral blood, including but not limited to TNFα, CRP, and IL-6, at baseline and following SBT777101 administration Change from baseline in phenotypic and molecular signatures in T cells and other immune cell subsets in peripheral blood and synovial tissue and/or fluid following SBT777101 administration
To assess immunogenicity of SBT777101	 Presence of circulating anti-drug antibodies (ADA) pre-dose and following SBT777101 administration Detection of cellular immunogenicity pre-dose and following SBT777101 administration
To evaluate the preliminary efficacy of SBT777101	 ACR20, ACR50 and ACR70 response rates following SBT777101 administration DAS28 scores and change from baseline in DAS28 scores following SBT777101 administration

3. STUDY DESIGN

3.1. Description of the Study

[figure not shown]
3.1.1. Overall Study Design

This is a Phase 1, open-label, study to evaluate the safety, tolerability, PK, PD, and preliminary clinical activity of single ascending doses of SBT777101 in patients with active RA.

Following screening, eligible subjects will undergo apheresis, and SBT777101 drug product will be manufactured for each subject. Each subject will receive a single dose of SBT777101 intravenously (IV) on study Day 1. Subject safety will be monitored acutely post dosing and throughout the study for 1 year. After one year and due to the use of lentivirus vector in SBT777101, all subjects will be encouraged to participate in a long-term safety follow-up (observational) study that will be conducted under a separate protocol in accordance with current FDA guidance.

The overall study design is displayed in Figure 1. A schedule of assessments (SoA) is provided in Appendix A and Appendix B.

Figure 1: Study Design

Dose Escalation Cohorts

The study will be open-label and employ a "3+3 Dose Escalation" design. Initially three eligible subjects will be evaluated in each cohort, enrolled for a safety monitoring period at least 14 days apart. Subjects will be monitored for dose limiting toxicities (DLTs) for at least 28 days following enrollment of the third or sixth subject.

- If a DLT is not seen in the first three subjects, then escalation to the next dose level may occur.
- If a DLT is seen in 1 of the first 3 subjects in any dose cohort, the cohort size will be expanded to six subjects. These additional subjects will be dosed at least 14 days apart and have a safety monitoring period of at least 28 days.
- If more than one DLT occurs in ≤6 subjects in a dose cohort, dose escalation will not occur, and this dose level will be identified as the non-tolerated dose. Otherwise, dose escalation may occur.

See Section 3.3 for definitions of DLTs and details of dose escalation rules.

Additional subjects may be screened and undergo apheresis at risk prior to the previous subject within a dose escalation cohort being dosed or completing their post dose safety monitoring period. These additional subjects will not receive treatment with SBT777101 until the safety monitoring period has been completed for the prior subject.

Dose escalation will be overseen by the study Safety Monitoring Committee (SMC; see Section 3.3).

Backfill Cohorts

At the Sponsor's discretion, additional eligible subjects (e.g., those beyond the initial 3 or 6 subjects initially treated as described above) may be enrolled into optional protocol-defined dose level "backfill" cohorts. Each backfill cohort will contain up to six subjects dosed at least 14 days apart. Backfill cohorts will not be opened until the dose escalation cohort at that dose level has been completed. Doses will not exceed the last cleared dose from the initial dose escalation cohorts.

Additional subjects may be enrolled at the Sponsor's discretion under the following conditions:

[figure not shown]

- Inability to manufacture the required dose of SBT777101 for any given subject, wherein the number of CAR positive T_{reg} cells is in the final drug product is insufficient for the assigned dose level. In this case, the subject may be enrolled into a backfill cohort at the highest possible cleared dose level (e.g., a subject intended for dose level 2 may be enrolled in dose level 1 backfill).
- Evaluation of PK, PD and biomarker data from a dose cohort indicates that additional data may better aid interpretation of preliminary PK and PD data and to guide future dose selection. Subjects may be added provided that the SMC does not indicate that doing so will present additional safety risks.

3.1.2. Subject Flow

The overall subject flow is displayed in Figure 2. Details of study assessments required during each study period are provided in the SoA (see Appendix A and Appendix B).

Figure 2: Subject Flow

DLT = Dose Limiting Toxicity; LTFU = long-term follow up; Wk = week Timing of the synovial biopsy and/or fluid collection for backfill cohorts may change based on evaluation of data from dose escalation cohorts

The study will consist of Screening, Pre-Treatment, Treatment and Safety Follow-Up periods. Details on study visits are provided in Section 7.1 and details on study assessments are provided in Section 7.2.

3.1.3. Starting dose and dose levels

Eligible subjects will be enrolled into sequential dose-level cohorts and will receive a single dose of SBT777101 by IV administration. Planned dose levels are shown in Table 1. Selection of dose levels for cohorts 2 and 3 will be overseen by the SMC in collaboration with the Sponsor.

Table 1: Planned Dosed During Dose Escalation

Planned dose	Total CAR ⁺ T cells (noted by EGFR expression)
1 (Starting dose)	100 x 10 ⁶
2	300×10^6
3 (Maximum dose)	900 x 10 ⁶

If a dose limiting safety event is observed the Sponsor may choose to enroll subjects into a cohort at a dose lower than 100×10^6 cells. Dose selection and initiation of this cohort would be overseen by the SMC.

Although three dose level cohorts are planned, fewer or additional cohorts may be included based on safety observations and/or study product manufacturing limitations. These additional dose levels will be lower than the maximum planned dose of 900×10^6 transduced cells. Determination of dose levels for additional cohorts will be overseen by the SMC in collaboration with the Sponsor.

3.2. Rationale for Study Design

3.2.1. Rationale for Study Population

Subjects with active RA have been chosen for this first in human study to assess the safety of SBT777101, a CAR T_{reg} specific for citrullinated proteins. Patients rather than healthy volunteers will be enrolled in this study as there is a clear potential for benefit of the drug treatment based on the known pathophysiology of the T_{regs} in this disease as demonstrated by previous clinical and preclinical data. Furthermore, healthy volunteers typically do not have chronic inflammation and are unlikely to have significant levels of citrullinated antigens that can activate SBT777101, limiting a full safety assessment of the cell product.

Eligible subjects will have active RA that is uncontrolled by FDA approved therapies and will have received prior treatment with at least two mechanistically different classes of b/tsDMARDs before being considered for inclusion. These are the patients with the greatest unmet need since they represent a treatment-refractory group. As such, SBT777101 treatment offers a novel option with the potential for treatment benefit.

The study will be open-label and employ a "3+3 Dose Escalation" design, with optional backfill cohorts. The open-label design will provide all subjects with the opportunity to receive active treatment with SBT777101 rather than placebo.

SBT777101 has been designed to target citrullinated proteins including vimentin, which can be further degraded to form the circulating peptide VICM. VICM levels are elevated in RA patients with active disease and are increased in patients with systemic inflammation as evidenced by elevated CRP (Drobinski et al., 2021; Mortensen et al., 2019). Taking this into consideration, this study has been designed to only enroll patients with active disease and all patients are required to have DAS28>3.1 (calculated using CRP) to be eligible. The relationship between levels of citrullinated proteins in the inflamed synovium and other biomarkers associated with local or systemic inflammation, including CRP and VICM, will be evaluated longitudinally in this trial to help inform inclusion criteria for future studies.

3.2.2. Rationale for Dose Selection and Escalation

3.2.2.1. Starting Dose

Given the lack of direct translatability to in vivo models, it is not possible to use a no observed adverse effect level (NOAEL) approach from nonclinical studies to determine the starting dose or an expected maximum dose level. The planned starting dose for the initial cohort in the Phase 1 study is $100 \times 10^6 \text{ CAR}^+\text{T}$ cells (noted by EGFR expression) administered by IV infusion. This low dose level is similar to the starting dose level administered to subjects in multiple clinical trials and case reports using polyclonal autologous and alloantigen-specific T_{reg} cellular therapy in disease indications including type 1 diabetes, graft versus host disease, kidney and liver transplantation, lupus and Crohn's disease (Bluestone et al., 2015; Chandran et al., 2017; Dall'Era et al., 2019; Desreumaux et al., 2012; Marek-Trzonkowska et al., 2014; Mathew et al., 2018; Roemhild et al., 2020).

Unlike prior T_{reg} products, SBT777101 includes addition of a CAR. While this introduces a modification to the cell, addition of the CAR to the T_{regs} is not expected to negatively alter the benefit-risk compared to untransduced cells. This is supported by data from studies with allo-antigen specific T_{regs}, where the potency of the allo-antigen T_{regs} is increased over that for polyclonal T_{regs} (Jiang et al., 2006; Golshayan et al., 2007). The increase in specificity of the T_{reg} via the T cell receptor did not lead to a change in safety profile compared to polyclonal T_{reg} therapies in clinical studies and the doses administered were within range of the proposed starting dose and were well tolerated. The starting dose level is also consistent with the doses of allo-antigen T_{reg} therapy previously given to transplant patients (Brunstein et al., 2011; Todo et al., 2016; Trzonkowski et al., 2009; NCT02474199, 2022).

3.2.2.2. Maximum Dose

The proposed maximum dose is 900 x 10^6 CAR⁺T cells (noted by EGFR expression) administered by IV infusion. The total number of T_{regs} to be given will be up to approximately 2.7×10^9 total T_{reg} cells, assuming a 30% CAR transduction efficiency rate. This is aligned with the maximum dose evaluated in polyclonal T_{reg} T1D study (2.6×10^9 total cells; (Bluestone et al., 2015) and below that tested in the kidney transplant study (5.0×10^9 total cells); (Mathew et al., 2018), both of which were well tolerated in these patient populations. This level of T_{regs} represents approximately 17% of the total T_{reg} pool in a human (T_{reg} and T_{reg} Lee, 2012). A small fraction (approximately 2%) of T_{regs} can be found in the bloodstream, with most cells being sequestered in the lymph nodes, intestine and bone marrow. It is therefore appropriate to dose up to the proposed level to ensure that sufficient study drug is present in the circulation to be able to traffic to the site of inflammation and reach the CAR target antigen within the synovial tissue.

3.2.2.3. Dose Escalation

Dose escalation to the next dose level will occur at least 28 days after the last subject in that cohort has been dosed.

The dose selected for the next cohort will be no more than 3-fold higher than that administered in the cleared cohort. This aligns with the dose escalation regimen utilized in other T_{reg} studies (Bluestone et al., 2015; Brunstein et al., 2011; Mathew et al., 2018; Roemhild et al., 2020).

3.2.3. Rationale for Pharmacokinetic and Immunogenicity Sampling Schedule

The frequent sampling schedule that follows the dosing of SBT777101 is designed to capture data at a sufficient number of timepoints to provide a detailed profile of the kinetics of SBT777101 in peripheral blood and to assess the presence of SBT777101- specific anti-drug antibodies (ADA) and their potential impact on kinetics and/or pharmacodynamic (PD) activity. Less frequent sampling will suffice to explore the induction of SBT777101-specific cellular immunogenicity (see Appendix A, Appendix B, and Appendix C).

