6.10. Overdose or Medication Error

For this study, any dose of SBT777101 greater than that designated in the cohort the subject was assigned to will be considered an overdose.

In the event of an overdose, the study site Investigator should:

- Treat all symptoms, as appropriate, and provide supportive care
- Contact the medical monitor immediately
- Closely monitor the subject for any AE/SAE and laboratory abnormalities
- Document the quantity of the excess dose as well as the duration of the overdose
- Obtain a serum sample for PK analysis as soon as practicable

Subjects who receive an overdose or for whom there is a medication error should remain in the study and continue to complete the study assessments.

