7.2.6.3. PK and Immunogenicity Assessments

Whole blood and serum samples will be collected to evaluate the pharmacokinetics and immunogenicity of SBT777101. This will include:

- Whole blood samples for PK analysis
- Serum samples for immunogenicity analysis will be collected to measure ADAs against the extracellular domain of the CAR and the EGFR tag.
- PBMCs will be collected to measure cellular immunogenicity against CAR-derived and EGFR tag-derived peptides.

In addition, the Sponsor may collect synovial tissue and fluid for analysis of presence of SBT777101.

The Sponsor may store samples for up to 15 years after the end of the study to achieve study objectives.

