APPENDIX B. SCHEDULE OF ASSESSMENTS: BASELINE AND SAFETY FOLLOW-UP PERIOD

	Safety Follow Up														UV	\mathbf{E}	
Study Week Study Day (visit window)	1					2	3 4		6 8		10	12	24	36	48/ES		T
	1	2	4 or 5	7 ±1	11 ±1	14 ±2	21 ±2	28 ±2	42 ±2	56 ±2	70 ±2	84 ±3	168 ±7	252 ±7	336 ±7		
Procedure		•		•				•	•				•	•			
SBT777101 administration	•																
Overnight stay/acute safety monitoring	•																
Patient self-temperature monitoring	•	•	•	•	•	•	•	•	•	•	•	•	•	•	•	•	•
Patient check-in (phone call, text etc) ^a		•	•	•													
Vital signs ^b	•	•	•	•	•	•	•	•	•	•	•	•	•	•	•	•	•
Adverse events ^c	•	•	•	•	•	•	•	•	•	•	•	•	•	•	•	•	•
Prior/Concomitant medications	•	•	•	•	•	•	•	•	•	•	•	•	•	•	•	•	•
Full physical exam				•				•		•					•		•
Directed physical exam	•	•	•		•	•	•		•		•	•	•	•		•	
Weight										•					•		•
12-lead triplicate ECG				•		•									•	•	•
Synovial biopsy for tissue								● ^{d,e}									•
Synovial fluid collection								●d,e				●d,e,f					•
Assessment of synovitis (clinical and/or ultrasound)								•				•					•
Urine pregnancy test	•											•	•		•		•
Lipid tests ^g															•		
Coagulation ^g													•		•		
Hematology ^g		•	•	•	•	•	•	•	•	•	•	•	•	•	•	•	•
Clinical chemistry ^g		•	•	•	•	•	•	•	•	•	•	•	•	•	•	•	•
Urinalysis ^g										•				•	•		•
Markers of inflammation h																•	
CRP		•		•		•	•	•	•	•	•	•	•	•	•	•	•
Joint count assessment (28 SJC/28 TJC)						•		•		•			•		•		•
Joint count assessment (66 SJC/68 TJC)												•					
Physician VAS						•		•		•		•	•		•		•
Subject VAS (global and assessment of pain)						•		•		•		•	•		•		•
HAQ-DI						•		•		•		•	•		•		•
FACIT-F													•		•		•
Blood samples for PK (ddPCR) i		•	•	•	•	•	•	•	•	•	•	•	•	•	•	•	•
Blood sample for cellular immunogenicity												•			•	•	•

FINAL Confidential

Version 1.0, 18-MAY-2022 Page 72 of 92

		Safety Follow Up				UV	ET										
Study Week			1			2	3	4	6	8	10	12	24	36	48/ES		
Study Day (visit window)	1	2	1 0 7 5	7	11	14	21	28	42	56	70	84	168	252	336		
	1	Z	4 or 5	±1	±1	±2	±2	±2	±2	±2	±2	±3	±7	±7	±7		
Procedure																	
Blood sample for ADA										•					•	•	•
Blood sample for exploratory inflammatory markers		•		•		•	•	•	•	•	•	•	•	•	•	•	•
Blood sample for ACPA/RF						•	•	•	•	•	•	•	•	•	•		•
Blood sample for VICM				•		•	•	•	•	•	•	•	•	•	•		•
Blood samples for exploratory biomarkers		•	•	•	•	•	•	•	•	•	•	•	•	•	•	•	•
Blood samples for RCL												•	•		•		

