ACPA = anti-citrullinated protein antibody; ADA = anti-drug antibody; CRP = C-reactive protein; ddPCR = droplet digital polymerase chain reaction; ECG = electrocardiogram; ES = End of Study; ET = early termination; FACIT-F = Functional Assessment of Chronic Illness Therapy – Fatigue; HAQ-DI = health assessment questionnaire disability index; PK = pharmacokinetic; RCL = replication competent lentivirus; RF = rheumatoid factor; SJC = swollen joint count; TJC = tender joint count; UV = unscheduled visit; VAS= visual analogue score VICM = citrullinated and MMP degraded vimentin fragment

Note: On Day 1, all assessments should be performed prior to dosing, unless otherwise specified.

- ^a Subjects should be contacted daily by the site (e.g by phone or text) following discharge through Day 7.
- ^b Vital signs must be measured approximately 15 minutes prior to infusion, then approximately every 15 minutes during the infusion.
- ^c After informed consent has been obtained but prior to initiation of study drug, only SAEs caused by a protocol-mandated intervention should be reported. After initiation of study drug, all AEs will be reported until the end of the study. After this period, the Sponsor should be notified if the investigator becomes aware of any SAE that is believed to be related to prior study drug treatment
- ^d The synovial biopsy/fluid collection can be performed at or up to 1 week after the scheduled assessment visit.
- ^e The timing of the synovial biopsy and/or synovial fluid collection in may be changed based on evaluation of data from the first dose escalation cohort.
- $^{\rm f}$ The synovial biopsy sample/fluid collection at Week 12 and at the ET visit is optional.
- g Tests included in laboratory assessments are described in protocol Appendix C.
- ^h A sample to test for markers of inflammation should be collected within 30 minutes of the onset of a suspected adverse event of infection or CRS.
- ⁱ The PK sample collected on study Day 2 should be collected at approximately the same time of day that the infusion of study drug took place on study Day 1 (+/- 1 hour). An unscheduled PK sample should be collected within 30 minutes of a suspected infusion related reaction adverse event.

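### ADA is sampled no more often than cellular immunogenicity, and not before Day 56, although Section 3.2.3 relies on frequent sampling; separately, Section 6.10 names the wrong matrix for the overdose PK sample

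*Protocol*

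**What the plan says.** **Purpose of the sampling.** Section 3.2.3 opens: "The frequent sampling schedule that follows the dosing of SBT777101 is designed to capture data at a sufficient number of timepoints to provide a" kinetic profile in peripheral blood, in detail. The same sentence gives a second purpose, to assess ADA, and the next sentence sets a contrast. The two meet in these words: "anti-drug antibodies (ADA) and their potential impact on kinetics and/or pharmacodynamic (PD) activity. Less frequent sampling will suffice". The measure for which less sampling is said to be enough is cellular immunogenicity.

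**Schedule.** Appendix A has one pre-dose ADA sample, between Days -10 and -4. In Appendix B the row "Blood sample for ADA" is marked on Days 56 and 336 and at unscheduled and early termination visits. The row "Blood sample for cellular immunogenicity" is marked on Days 84 and 336 and at the same two extra visit types. PK by ddPCR is marked at every scheduled visit from Day 2. Footnote i fixes the first one: "The PK sample collected on study Day 2 should be collected at approximately the same time of day that the infusion of study drug" was given on Day 1, within an hour either way.

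**Use of the data.** Section 9.7.4 derives Tmax, Cmax, AUC0-28 and Clast by non-compartmental methods and summarizes the proportion of ADA-positive subjects over time and by dose level.

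**Matrix for PK.** Section 7.2.6.3 lists "Whole blood samples for PK analysis" and assigns serum to ADA. Section 9.4.2.1 defines PK through CAR transgene levels in peripheral blood. Section 6.10, on overdose, says: "Obtain a serum sample for PK analysis as soon as practicable".

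**The concern.** Section 3.2.3 is the only justification given for the ADA schedule, and it describes something that Appendix B does not contain. If circulating cells fall away in some subjects between, say, Day 14 and Day 42, a natural question is whether an antibody response came first. With no scheduled post-dose ADA sample before Day 56, the data could not show when ADA appeared relative to that loss. Section 3.1.1 lets PK, PD and biomarker data prompt added backfill subjects and guide future dose selection, so the reading of early exposure matters even though these endpoints are exploratory. Samples not taken early cannot be recovered later.

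The overdose instruction has a similar cost on a smaller scale. The product is cells, and serum is the fraction left once cells and clot are removed. A site that follows Section 6.10 literally would draw a largely cell-free sample at a moment that cannot be repeated.

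**Working it through.** **Step 1. Read the Appendix B rows.** The scheduled columns are Days 1, 2, 4 or 5, 7, 11, 14, 21, 28, 42, 56, 70, 84, 168, 252 and 336 (15 visits), followed by unscheduled and early termination. As a check that the marks line up with the columns, the full physical examination falls on 4 scheduled visits (Days 7, 28, 56, 336) and the directed examination on the other 11, with no overlap: 4 + 11 = 15.

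| Measure | Scheduled post-dose days | Number | First |
|---|---|---|---|
| PK | 2, 4 or 5, 7, 11, 14, 21, 28, 42, 56, 70, 84, 168, 252, 336 | 14 | Day 2 |
| ADA | 56, 336 | 2 | Day 56 |
| Cellular immunogenicity | 84, 336 | 2 | Day 84 |

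The measure that Section 3.2.3 calls less frequent is sampled as often as ADA.

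**Step 2. Compare ADA with PK.**
- To Day 28: PK on Days 2, 4 or 5, 7, 11, 14, 21 and 28 = 7 samples; scheduled post-dose ADA = 0.
- Before Day 56: 7 + 1 (Day 42) = 8 of the 14 PK samples.
- Scheduled post-dose days with both PK and ADA: Days 56 and 336 only.

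**Step 3. Compare ADA with the biopsy.** The Week 4 biopsy belongs to Day 28 (±2 days) and may be done up to 1 week later, so at the latest on Day 28 + 2 + 7 = 37. The first scheduled post-dose ADA sample is at the earliest on Day 56 - 2 = 54. The gap is at least 54 - 37 = 17 days.

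**Step 4. Are there draws to use?** On Days 14, 28 and 84, Appendix B already takes hematology, chemistry, CRP, PK and exploratory marker samples. ADA serum there needs no new visit or venepuncture.

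**Step 5. Overdose matrix.** PK analyte: CAR transgene (Section 9.4.2.1). Assay: ddPCR (Appendix B). Matrix: whole blood (Section 7.2.6.3). Section 6.10 alone says serum for PK. No second, serum-based PK assay is described.

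**Step 6. The first day of PK.** Day 2 sampling at 24 ± 1 h puts the earliest scheduled post-dose value at 23 h, so Tmax from scheduled samples cannot be under about 23 h. Whether this affects Cmax and AUC0-28 depends on kinetics that the protocol does not give. As an illustration only, assume a peak at the end of infusion, mono-exponential decline with half-life h days, a zero pre-dose value and the linear trapezoid at 0, 1, 3.5, 6, 10, 13, 20 and 27 days after infusion. With k = ln 2 / h, observed over true Cmax is 2^(-1/h), and the true AUC is (1 - e^(-27k))/k.

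| Assumed h (days) | Observed/true Cmax | Observed/true AUC0-28 |
|---|---|---|
| 0.25 | 6% | 30% |
| 1 | 50% | 80% |
| 3 | 79% | 92% |
| 7 | 91% | 96% |
| 14 | 95% | 97% |

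The answer runs from serious to negligible according to the assumption. If the true peak comes after Day 2 through expansion, Cmax and Tmax are little affected.

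**The case against.** **ADA impact is not an endpoint.** This is correct. The immunogenicity endpoints are ADA presence and detection of cellular immunogenicity, all exploratory and summarized descriptively. The effect of ADA on kinetics appears only as a purpose in Section 3.2.3. That lowers the stakes, but it leaves a stated purpose that the schedule does not serve.

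**Frequent may be meant for PK only.** The sentence could be read that way, but it joins ADA to the same schedule, and the next sentence singles out cellular immunogenicity as the less frequent measure.

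**ADA can still be linked to kinetics.** Much of this stands. A reader might infer that no such link is possible, and the protocol does not support that. The pre-dose sample lets pre-existing ADA be related to the whole PK profile, a Day 56 result can be set against the same subject's earlier PK, and unscheduled and early termination visits add ADA samples. The optional Week 12 fluid collection follows the Day 56 sample, and Appendix B allows biopsy timing to change after the first cohort. What is lost is the timing of treatment-emergent ADA before Day 56.

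**The PK schedule is adequate.** This also stands. A reader might infer from the empty first day that the schedule cannot give a detailed PK profile, or that exposure will be understated by a large and known factor. Fourteen post-dose samples do give a detailed profile from about 24 hours, and Section 3.2.3 promises no end-of-infusion sample. The figure of about 2% of Tregs in blood (Section 3.2.2.2) describes where such cells normally reside; it does not say how fast infused cells redistribute. Section 1.6.1 reports proliferation on antigen, so a later peak is possible. How time zero enters the AUC can be left to the SAP.

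**The overdose wording is a separate matter.** It is: it conflicts with Sections 7.2.6.3 and 9.4.2.1 and has no bearing on Section 3.2.3. It remains wrong as written.

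**Conclusion.** The point holds in two parts, neither of which needs a model.

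1. Section 3.2.3 and the ADA row of Appendix B do not agree. The shortfall is zero scheduled post-dose ADA samples against seven PK samples in the AUC0-28 window, and a first ADA result at least 17 days after the latest time allowed for the Week 4 biopsy as currently scheduled. This rests only on the column positions in Appendix B, which pass the alignment check.
2. The serum PK sample in Section 6.10 conflicts with the PK matrix and assay defined elsewhere in the protocol.

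The missing Day 1 PK sample is a limitation to acknowledge. It bounds observed Tmax at about 23 hours and touches Cmax and Tmax materially only if the peak is early; the documents give no kinetics from which to put a size on it.

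Overall this is a moderate point that should be corrected: the endpoints are exploratory, the remedy is cheap, and early samples cannot be taken afterwards.

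**What to change.** - **ADA.** Add ADA serum to existing draws in Appendix B, for example on Days 14, 28 and 84. Cost: about three tubes and three assays per subject, at most 3 × 36 = 108 if all 36 planned subjects are dosed and attend, with no added visit. If samples are not added, reword Section 3.2.3 to say that ADA is sampled at Weeks 8 and 48 and that onset before Week 8 will not be timed.
- **Overdose sample.** In Section 6.10, change serum to whole blood for the PK sample so that it agrees with Sections 7.2.6.3 and 9.4.2.1 and Appendix B. Cost: a wording change.
- **Optional.** Consider one whole-blood PK tube after the end of infusion on Day 1, during the stay of at least 24 hours that Section 8.1 already requires. Cost: one draw and one assay per subject. If it is not added, state when reporting Tmax and Cmax that the first scheduled post-dose sample is at about 24 hours.
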